4.1.3 End of Treatment

When the subject permanently discontinues study drug, the end of treatment (EOT) visit should be conducted. If the EOT visit coincides with a regular study visit, the EOT evaluations will supersede those of that scheduled visit, and the data should be entered in the EOT visit in the eCRF. The subject should be encouraged to return for the follow-up visit.

4.1.4 Safety Follow-up:

The safety follow-up period is the interval between the EOT visit and the scheduled follow-up visit, which should occur 30 to 35 days after the EOT visit (or after the last dose of study drug if the EOT visit was not performed). Adverse events and SAEs must be reported until at least 30 days after the last dose of study drug; or until toxicities resolve, return to baseline, or are deemed irreversible; death; or initiation of a new anticancer treatment, whichever occurs first. Reasonable efforts should be made to have the subject return for the follow-up visit and report any AEs that may occur during this period.

If a subject is scheduled to begin a new anticancer therapy before the end of the 30-day safety follow-up period, the safety follow-up visit should be performed before new anticancer therapy is started. Once new anticancer therapy has been initiated, the subject will move into the survival follow-up period.

4.1.5 Disease Status Follow-up:

Subjects who discontinue study treatment for a reason other than disease relapse or progression will move into the disease status follow-up period and should be assessed every 12 weeks by radiologic

imaging to monitor disease status. Every effort should be made to collect information regarding disease status until:

- The start of new antineoplastic therapy.
- Disease relapse or progression.
- Death.
- The end of the study.

At disease relapse or progression, a biopsy and subsequent genomic sequencing at the sponsors central laboratory is recommended after written informed consent of the patient.

4.1.6 Survival Follow-up:

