Once a subject has confirmed disease relapse or progression, or starts a new anticancer therapy, the subject moves into the survival follow-up period and should be contacted by telephone, email, or visit at least every 12 weeks to assess for survival status until death, withdrawal of consent, or the end of the study, whichever occurs first. The investigator or qualified representative can also use continuing subject records to report data on subsequent treatment regimens, and overall survival in the eCRF.

4.1.7 End of Study:

The end of the study may be designated as the timepoint when all subjects have discontinued the study after 2 years of follow-up or when the sponsor terminates the study.

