7. STATISTICAL CONSIDERATIONS

7.1 Patient Accrual, Study Duration and Calculation of Patient Numbers

The recruitment period will be 2 years and patients will be followed for an additional 2 years or until relapse or progression. 2-Year relapse-free survival (RFS) rate is the primary endpoint. No interim analyses are planned. Patients will be consecutively molecularly screened and enrolled into the study. It is expected that about 35% of the total screened patients will be eligible and will be enrolled in this study to receive Pemigatinib treatment. Treatment will be continued for a maximum period of 12 months or until the evidence of disease relapse or unacceptable toxicity development. The assumption is that treatment with Pemigatinib will result in a significant higher 2-year RFS rate at 2 years of 45% RFS compared to the reported 30% RFS at 2 years in bladder cancer patients [3].

Statistical Power Calculations:

In an exact single-stage phase II design [24] with power: 0.80; one-sided alpha: 0.10; H0: 2-year RFS: 30%; H1: 2-year RFS: 45% and follow-up duration of 2 years, the total number of eligible and treated patients needed to be enrolled is 50. Patients who withdraw from the study before completing the study period of 2 years, cannot be included in the calculation of the 2-year RFS rate. We estimate that ~15% of the patients will be withdrawn. Therefore, we need a total of 56 patients enrolled. Cut-off to reject the alternative hypothesis H1 is a total of 20 or more patients who experience relapse or progression at or before 2 years of study follow up.

A total of 56 patients needed in this phase II trial is corresponding to approximately 150 patients needed for molecular pre-screening. The primary analysis includes the planned analysis of the primary endpoint 2-year RFS rate which will be analyzed at the 2-years follow-up time point. RFS is defined as the time from the date of start of treatment until disease relapse or progression by investigator determination, or death due to any cause, whichever occurs first. See also 4.4.3.

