7.4.3 Overall Survival Analysis

Overall Survival (OS) is defined as the time from the date of start of study treatment to death due to any cause. Participants without documented death at the time of analysis will be censored at the date of the last follow-up. Overall survival will be analyzed and graphically presented by the Kaplan-Meier method. The percentage of patients who survive at 2 years will be calculated with its 95% Confidence Interval.

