Appendix 6 Flowchart and Laboratory Evaluations.

	Pre-surgery	Sur-gery	Screeni ng	Treatment period 12 months				End of Treatme nt (EOT)	Follow up after treatment 12 months		
				First 3 weeks after start of treatment			Q 3 weeks*		Safety	Disease status	Survival status
				Day 1 enrollment	Day 8 (± 3 days)	Day 15 (± 3 days)	Day 21 (± 3 days), etc		EOT + 30-35 days	Every 12 weeks	Every 12 weeks
Inf.Consent	X		X								
Selection criteria	X		X	X							
Tumor Tissue for genomic profiling			X								
Demographics & Med. History			X								
Phys. Exam. & NYHA status			X								
WHO PS			X	X			X	X		X	
ECG			X				X q12 wks	Prev. Abn.	Prev. Abn.		
Hematology & Biochemistry			X	Repeated only if done > 14 days prior to day 1	X	X	X q3 wks*	Prev. Abn.	Prev. Abn.		
Urine / Serum Pregnancy test (females of childbearing potential)			X	X	Only in case of susp. pregnancy						
Urinalysis, Coagulation, Lipid and Endocrine Panels			X				X ***	Prev. Abn.	Prev. Abn.		
CT / MRI chest/abdomen/pelvis Q 12 weeks**			X				X q12 wks			X	
Ophthalmological investigations every 12 weeks			X				X q12 wks	Prev. Abn.			
Study drug dispensing and accountability				X			X	X			
Concomitant medication			X	X	X	X	X	X	X		
Adverse events (CTCAE v4.0)					X	X	X	X	X	X only study or drug related SAEs	X only study or drug related SAEs
Survival data											X

Prev. Abn.: Only in case of abnormalities at previous, latest test or examination.

* Timing of subsequent visits and laboratory examinations can be prolonged to max. 9 weeks intervals if no problems exist during the first 12 weeks of therapy.

** CT / MRI every 12 weeks +/- 1 week. At disease relapse or progression, a biopsy and subsequent genomic evaluation is recommended.

*** Urinalysis, Coagulation panel, Lipid panel and Endocrine panel (next page): repeat at 3 weeks and only in case of (persistent) abnormalities repeat q3 weekly; EOT and Safety EOT + 30 days only in case of previous, latest test abnormalities.

Laboratory test to be performed in the local laboratory at each hospital. Other than hematology and chemistry lab tests: Hepatitis screening only at screening, if not done already before radical surgery.

Urinalysis, Coagulation panel, Lipid panel and Endocrine panel: repeat at 3 weeks and only in case of (persistent) abnormalities repeat q3 weekly; EOT and Safety EOT + 30 days only in case of previous, latest test abnormalities.

Hematology	Chemistry	Urinalysis	Other
Hematocrit	Total protein	Occult Blood	Hepatitis serology

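### Appendix 6 ends follow-up 12 months after treatment, in conflict with the body text; read literally, early stoppers leave the visit schedule before the 2-year RFS and OS time point

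*Combined protocol and SAP*

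**What the plan says.** Appendix 6 sets out a "Treatment period 12 months", then an end-of-treatment visit, then a block headed "Follow up after treatment 12 months". That block holds the safety column and the 12-weekly disease-status and survival columns.

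The body text defines follow-up by stopping events:

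- **Section 4** counts RFS and OS from first dose, puts the final RFS assessment at 2 years, continues survival assessment after relapse, and then refers the reader to Appendix 6.
- **Section 4.1.5**: "Subjects who discontinue study treatment for a reason other than disease relapse or progression will move into the disease status follow-up period", with imaging every 12 weeks. It goes on: "Every effort should be made to collect information regarding disease status until" new antineoplastic therapy, relapse or progression, death, or the end of the study.
- **Section 4.1.6** requires contact at least every 12 weeks "to assess for survival status until death, withdrawal of consent, or the end of the study, whichever occurs first".
- **Section 4.1.7** allows the end of study to be set when "all subjects have discontinued the study after 2 years of follow-up", or when the sponsor terminates the study.
- **Section 5.4** keeps patients who stop for toxicity in disease and survival follow-up, and keeps relapsed patients in survival follow-up.
- **Section 7.1**: "patients will be followed for an additional 2 years or until relapse or progression".
- **Section 7.4.3**: "The percentage of patients who survive at 2 years will be calculated".

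**The concern.** Both time-to-event endpoints need each patient's status at month 24 from first dose. The flowchart header counts from the end of treatment, so its window shortens month for month with early stopping. The protocol itself points to that table for the RFS and OS schedule, so a site could reasonably book visits from it.

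The patients affected would not be a random subset. For RFS they are those who stopped for toxicity or by choice. For OS they also include those who relapsed on treatment, who are the most likely to die. If their visits ended early, relapses and deaths before month 24 could go unrecorded, and censoring at the last visit would be related to prognosis. Missed scans cannot be recovered afterwards.

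**Working it through.** **Inputs.** Treatment 12 months and follow-up after treatment 12 months (Appendix 6). 2-year RFS 30% under H0 and 45% under H1, one-sided alpha 0.10, power 0.80, 50 evaluable and 56 enrolled (section 7.1). The documents give no early-stopping rate.

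**1. The plan's own figures.** For a patient who completes treatment, 12 + 12 = 24 months, so the header fits the 2-year time point in that case. The exact single-stage design also reproduces: n = 50 with at least 20 relapse-free gives alpha 0.0848 and power 0.8026.

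**2. Header read literally.** Scheduled end = t + 12, where t is the month of stopping. Gap = 24 − (t + 12) = 12 − t.

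| Stop at month | Schedule ends | Gap to month 24 (months) | 12-weekly visits lost (about) |
|---|---|---|---|
| 1 | 13 | 11 | 4 |
| 3 | 15 | 9 | 3 |
| 6 | 18 | 6 | 2 |
| 9 | 21 | 3 | 1 |
| 12 | 24 | 0 | 0 |

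**3. Body text.** Under sections 4.1.5 to 4.1.7 the gap is 0 for every month of stopping, apart from the listed stopping events and early termination by the sponsor.

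**4. What the literal gap could hide for RFS.** Assume a constant hazard. For a patient event-free at month t + 12, the chance of an event before month 24 is 1 − S^((12 − t)/24), where S is the 2-year RFS.

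- t = 3: 1 − 0.45^(9/24) = 0.259; 1 − 0.30^(9/24) = 0.363.
- t = 6: 1 − 0.45^(6/24) = 0.181; 1 − 0.30^(6/24) = 0.260.

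**5. Ceiling for OS through relapse.** The chance of an RFS event by month 12 is 1 − S^(1/2).

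- S = 0.45: 0.329, and 0.329 × 56 = 18.4 patients.
- S = 0.30: 0.452, and 0.452 × 56 = 25.3 patients.

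These 18 to 25 patients are expected first-year RFS events, not patients with missing OS. They include deaths, which are already OS events, and relapsed patients whose death would fall inside the 12-month window.

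**6. Scale if evaluable patients were lost.** The numbers lost are assumed, and the cut-off is re-chosen at each n to keep alpha at or below 0.10.

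| Evaluable of 56 | Relapse-free needed | Alpha | Power |
|---|---|---|---|
| 50 | 20 | 0.085 | 0.803 |
| 47 | 19 | 0.083 | 0.781 |
| 44 | 18 | 0.081 | 0.756 |
| 41 | 17 | 0.079 | 0.728 |

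The plan does not prescribe such a loss. These figures also treat the loss as random, so they do not measure bias.

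**7. How firm the body text is.** Section 4.1.7 gives its 2 years no start point. Counted from first dose or from end of treatment, they reach month 24 or later; counted from an earlier date such as surgery, they fall short. Section 8.6 defines the end of study differently, as the last visit of the last patient, and for late enrollees Appendix 6 helps to set that visit. Section 5.4 only encourages patients who stop early to attend their remaining visits. No sentence requires status through month 24 from first dose whatever the date of stopping, and none says which section prevails.

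**The case against.** The strongest reply is that the header is only the nominal layout for a patient who completes treatment, and that the body text deals with early stoppers directly. Section 4.1.5 is written for them and sets no 12-month limit. Sections 4.1.6 and 5.4 continue survival contact after relapse. The synopsis timeline also fits: centre initiation in April 2020 and last follow-up in April 2024 make 48 months, which is 24 of recruitment plus 24 of follow-up. All of this stands, and it rules out three stronger readings.

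- A reader might infer that 2-year RFS and OS will not be observed in early stoppers. The documents do not support that, because sections 4, 4.1.5, 4.1.6 and 5.4 all prescribe continued follow-up.
- A reader might infer from section 7.1 that OS collection ends at relapse. The clause read alone says so, but sections 4, 4.1.6 and 5.4 say the opposite, and the clause stands directly before the RFS endpoint is named.
- A reader might infer that early stoppers are dropped from the primary rate. Section 7.1 excludes patients who withdraw from the study, and section 5.4 separates stopping the drug from leaving follow-up.

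The reply does not remove the conflict. The header puts a 12-month length on columns that the body text leaves open to the end of the study, and section 4 refers to that table for the schedule.

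**Conclusion.** The Appendix 6 header contradicts sections 4, 4.1.5 to 4.1.7 and 5.4 on how long disease status and survival are followed after early stopping. Section 7.1 adds a second ambiguity on follow-up after relapse. The loss of 2-year status is a risk that depends on sites following the flowchart.

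Its overall size cannot be derived without an early-stopping rate. For an individual patient under a constant hazard, the chance of an unseen RFS event is 26% to 36% for a stop at month 3 and 18% to 26% for a stop at month 6. The 18 to 25 of 56 is only an upper bound, in expectation, on patients whose survival contact could end early because of a first-year relapse. This is a minor to moderate inconsistency in the observation window of the primary endpoint, with no change to sample size or planned power.

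**What to change.** Reconcile the passages with three wording changes:

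1. **Appendix 6 header:** disease-status follow-up (until relapse or another stopping event in section 4.1.5) and survival follow-up until at least 24 months from first dose, regardless of when treatment stopped.
2. **Section 4.1.7:** state that the 2 years of follow-up are counted from first dose.
3. **Section 7.1:** apply the relapse or progression clause to disease-status imaging only, so that it does not read as ending survival follow-up.

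Section 4.1.5 also stops imaging at the start of new antineoplastic therapy. That is a separate matter, which this fix leaves unchanged.

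The cost is one table header and two sentences, handled as an amendment under section 8.4. Any additional scans and contacts for early stoppers are those that sections 4.1.5 to 4.1.7 already imply. No extra patients are needed.
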